6.5.3.2 COVID-19 Pandemic Population

The COVID-19 pandemic population includes subjects who were discontinued or were lost to follow-up due to COVID-19 complications or pandemic concerns, or subjects that had significant COVID-19 related protocol deviations. The subjects in the COVID-19 pandemic population will be presented in an accountability table.

6.5.4 Demographic and Other Baseline Characteristics

6.5.4.1 Demographic Variables

The demographic variables collected in this study include age, sex, childbearing potential (if female), race, and ethnicity. Subjects who record more than one race will be grouped into a single category denoted as Multi-racial.

Age (years) will be summarized using continuous descriptive statistics. Age will also be categorized as follows: <65 years and ≥ 65 years.

The number and percentage of subjects will be presented for age category, sex, childbearing potential (for female subjects), study eye, race, and ethnicity. The demographic variables will be summarized for all treated eyes. A data listing by subject will be provided that includes all demographic variables.

6.5.4.2 Baseline Refractive Parameters

The preoperative bin distribution of enrolled eyes by sphere and cylinder is based on the preoperative manifest refraction, specifically sphere and cylinder. All eyes will be treated for myopia with a target refraction of emmetropia. All eyes enrolled and treated will have at least -1.0 D of spherical myopia or more and at least 0.0 D or more of cylinder in the study. Table 1, above, provides the expected bin distribution stratified by preoperative sphere and cylinder. Tables will be provided of preoperative bin distributions for all treated eyes, eyes treated for spherical myopia, and eyes treated for astigmatic myopia. A data listing of preoperative sphere and cylinder by subject also will be provided. Sphere and cylinder values will be converted to minus notation for presentation and subsequent analysis in the efficacy section as follows:

If the Original Cylinder <= 0, then no conversion is necessary.

If the Original Cylinder > 0 then

New Sphere = Original Sphere + Original Cylinder

New Cylinder = - Original Cylinder

New Axis = Original Axis - 90, if Original Axis > 90

Original Axis + 90, if Original Axis \leq 90

6.5.4.3 Preoperative Procedure Variables

Preoperative clinical procedure data collected at the Preoperative Visit, including the Schirmer's test, manifest refraction, keratometry, corneal topography, pupil size, uncorrected near visual acuity (UCNVA), UCDVA, distance BSCVA, slit lamp examination, pachymetry, cycloplegic refraction, endothelial cell density, contrast sensitivity, and dilated fundoscopic examination for ophthalmic assessments, and intraocular pressure (IOP) will not be summarized but will be listed.

6.5.4.4 Operative Procedure Variables

Parameters of the LASIK surgery, including treatment type, targeted refractive outcome, optical zone (mm), LASIK ablation (microns), central ablation depth (microns), maximum

ablation depth (microns), method of flap creation, anticipated flap thickness (microns), anticipated flap diameter (mm), treatment interruption, and problems during surgery, will not be summarized but will be listed.

6.5.4.5 Ocular Medical History

Ocular medical history will be coded using Medical Dictionary for Regulatory Activities (MedDRA), Version 22.0. Ocular medical history will not be summarized but will be listed.

6.5.5 Concomitant Medications

Concomitant medications are medications listed for a subject as having been taken (1) prior to LASIK surgery and continuing for any time following the surgery or (2) at any time following LASIK surgery. Concomitant medications will be coded using World Health Organization Drug Dictionary (WHODrug) terminology, Version B3 Global March 2019. However, medications will not be summarized in tables.

In addition, the Investigator may use any medication that is judged necessary, appropriate, and beneficial to the subject. Documentation of all such medications used by the subject during this study for the treatment of operative eyes (with the exception of the surgeon's standard regimen for pre-, intra-, and post-operative medications) will be made on the appropriate sections of the electronic case report forms (eCRFs).

A data listing by subject that includes all concomitant medications will be provided. The concomitant medication listing will not contain information on non-drug therapies.

6.5.6 Analysis of Effectiveness Endpoints

6.5.6.1 Descriptive Statistics and Data Preparation

Statistical programming and analyses will be performed using SAS® Version 9.4 or higher. Output will be provided in rich text format (RTF) for tables and portable document format (PDF) for tables, data listings, and figures using landscape orientation. All study data will be listed by subject, eye, and visit (as applicable) based on all treated subjects unless otherwise specified.

Summaries for continuous and ordinal variables will include the number of observations (n), arithmetic mean, standard deviation (SD), median, minimum, and maximum. Minima

and maxima will be reported with the same precision as the raw values; means and medians will be presented to one additional decimal place than reported in the raw values. Standard deviations will be presented to two additional decimal places than reported in the raw values. Summaries for discrete variables will include counts and percentages. All percentages will be rounded to one decimal place (i.e., XX.X%).

When summarized by visit, nominal visits as indicated on the case report forms will be used. Visit windows will not be considered in the presentation of data by visit.

All statistical tests will be one-sided with a significance level of 0.025 ($\alpha = 0.025$) unless otherwise specified.

Confidence intervals (CIs) around single estimated proportions will be two-sided at 95% confidence.

All p values will be rounded to 4 decimal places; p-values less than 0.0001 will be presented as "<0.0001"; p-values greater than 0.9999 will be presented as ">0.9999."

Unless otherwise specified, summaries will be presented by visit, where appropriate. Data listings will be sorted by subject number, eye, visit/time point, and parameter as applicable.

Baseline is defined as the last measurement prior to LASIK surgery. Change from baseline will be calculated as post-baseline visit minus baseline visit.

Eyes will be treated as independent sampling units ignoring any correlation between the two eyes of each subject, as is customary for LASIK clinical trials.

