11.	Use chronic medications by any administration route that may increase risk to the subject or may confound the outcome of the study, including those known to affect wound healing (e.g., corticosteroids, antimetabolites, etc.).	
12.	Are known to have acute or chronic disease or illness (e.g., dry eye, cataract, glaucoma, immuno-compromised, rheumatoid arthritis, clinically significant atopic disease, acne rosacea, etc.) that would increase operative risk or confound the results of the study.	
13.	Are taking medications contraindicated with LASIK such as isotretinoin (Accutane) or amiodarone hydrochloride (Cordarone).	
14.	Are known to be pregnant, lactating, or who plan to become pregnant during the course of the study.	

Bausch + Lomb Study #884	
	15. Have known sensitivity to medications used for standard LASIK.
	16. Have the presence of systemic disease likely to affect wound healing, e.g., autoimmune disease, systemic connective tissue disease, diabetes, or severe atopic disease.
	17. Are participating in any other ophthalmic clinical trial within30 days of screening or during this clinical trial.
	 Have an ocular muscle disorder including a strabismus or nystagmus, or other disorder affecting fixation.
	19. Have a history of or evidence of glaucoma or are a glaucoma suspect.
	20. Eyes with mesopic pupil size > 7.0 mm.
	21. Have a Schirmer's pre-operative test without anesthesia < 4 mm/5 minutes
Planned Study Period and Duration of Treatment	Enrolled subject eyes will undergo LASIK surgery and will be followed for approximately nine months after surgery.
Test Medical Device	Technolas TENEO 317 Model 2 excimer laser is a scanning excimer laser that operates at 193 nm ultraviolet wavelength to photoablate corneal tissue in order to achieve a refractive change.
Study Effectiveness Endpoints	 The percentage of eyes that achieve predictability (attempted versus achieved) of MRSE within ± 0.50 D The percentage of eyes that achieve predictability (attempted versus achieved) of MRSE within ± 1.00 D The percentage of eyes targeted for emmetropia that achieve a UDVA of 20/40 or better
Statistical Methods	Continuous measures will be summarized by the mean, standard deviation, median, minimum, and maximum. Categorical and incidence measures will be summarized by both count and percentage.
	Following multiple imputations of missing data, each primary endpoint will be compared to a corresponding null proportion using a binomial test.

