5. STUDY DESIGN

5.1 Justification of Study Design

The TENEO 317 Model 2 excimer laser workstation received CE Mark status in Europe in 2017 and is currently running version 1.28 software (SW). The difference between the EU version 1.28 and the version 1.28 US SW is that the version 1.28 US SW will have software treatment capabilities other than myopic LASIK with or without astigmatism that will be disabled on all Technolas TENEO 317 Model 2 systems to be used in this myopia/myopic astigmatism study.

A retrospective post-CE Mark chart review provides evidence of the safety and effective performance of the TENEO 317 Model 2 excimer laser running PROSCAN ver. 1.27.2 SW for completing LASIK surgeries on myopic eyes with or without astigmatism through 1 month of follow-up with 518 eyes treated at 10 sites in Europe, Middle East and Africa.³³ Of the 518 eyes enrolled in the chart review, 72 eyes had spherical myopia and 446 eyes had myopic astigmatism.

In the chart review report, 93% of subject eyes were 20/20 or better at ≥ 1 mo, and 99% were 20/32 or better at ≥ 1 mo. Further, 100% of subject eyes had uncorrected distance visual acuity of 20/40 or better post-surgery.

The Technolas TENEO 317 Model 2 aspheric ablation PROSCAN version 1.27.2 software was the subject of a post-market study that demonstrated excellent results for spherical correction and showed a slight under-correction for cylinder. As a result, the laser's internal cylinder conversion factor for the PROSCAN version 1.27.2 software was increased to compensate for cylindrical under-correction, while the spherical correction component remained unchanged. The resulting revised aspheric ablation PROSCAN version 1.28 US software is the subject of this study.

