4 INTRODUCTION

The purpose of this statistical analysis plan (SAP) is to describe the planned analyses and reporting for clinical study Bausch & Lomb 884 conducted according to TENEO 317 Clinical Investigation Plan, Version 8.0, dated 19 November 2020.

This SAP is being written with due consideration of the recommendations outlined in the most recent International Conference on Harmonisation (ICH) E3 Guideline (July 1996), entitled Guidance for Industry: Structure and Content of Clinical Study Reports.

This SAP describes the data that will be analyzed and the subject characteristics, device effectiveness, and safety assessments that will be evaluated.

This SAP provides details of the specific statistical methods that will be used. The statistical analysis methods presented in this document will supersede the statistical analysis methods described in the clinical protocol. If additional analyses are required to supplement the planned analyses described in this SAP, they will be completed and will be identified in an amended SAP (approved prior to database lock) or in the clinical study report.

Device Description

The Technolas Teneo 317 Model 2 (ver. 1.28 US software [SW]) excimer laser is a scanning excimer laser that operates at 193 nm ultraviolet wavelength to photoablate corneal tissue and employs a proprietary aspheric ablation profile rather than a conventional "Munnerlyn" ablation profile. By scanning a small diameter beam (1 mm in diameter) in a random raster pattern, the Teneo 317 Model 2 (ver. 1.28 US SW) excimer laser offers the following advantageous features:

- Flexible treatment patterns for the treatment of myopia,
- Wide ablation zones (up to 7 mm), and
- A smooth ablation-surface.

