6 INVESTIGATIONAL PLAN

6.1 Overall Study Design

The design of this clinical study is a prospective, open-label, multicenter, non-randomized clinical investigation, where the effects of LASIK in correcting myopia and myopic astigmatism are evaluated by comparing postoperative refraction and visual acuity to performance standards. The study treatment range (indication for use) includes up to manifest refraction spherical equivalent (MRSE) of -11.50 diopters (D).

The study will involve an evaluation of approximately 334 treated eyes at up to 12 investigational sites, with a final sample size of at least 300 study eyes evaluable at the final visit. Every effort will be made to enroll approximately the same number of eyes at each investigational site. The additional 34 study eyes will allow for losses up to 10% due to early subject discontinuation. Both eyes of a subject may be enrolled. Subjects will be permitted to have both eyes enrolled so long as both eyes meet all inclusion/exclusion requirements. Analyses will include all enrolled eyes treated with the TENEO 317 laser. Enrollment will be limited to subject eyes with sphere of -1.0 D up to -10.00 D, cylinder between 0.0 D and -3.0 D, and with a spherical equivalent (SE) between -1.0 D and -11.50 D. Enrolled subjects can possibly attend up to 8 scheduled study visits. It is planned to enroll and treat approximately 334 subject eyes, with an expectation that approximately 300 study eyes will complete post-surgical follow-up for 9 months. All subjects, regardless of the time of individually achieving refractive stability, will be followed up until the last study visit (Visit 8) which is Month 9 postoperatively.

For completed subjects, it is planned to have ≥ 20 eyes per each dioptric bin (see **Table 1**) of spherical correction to be studied and ≥ 30 eyes per dioptric bin of cylinder correction

to be studied. Of the eyes in the -0.25 to -1.0 D astigmatism range, at least 30 eyes are planned to be in each of the -0.25 to -0.5 D and the -0.5 to -1.0 D astigmatism ranges (see **Table 1**, Bin Table).

A 180-Day PMA supplement application will be submitted to the U.S. FDA when the enrolled study cohort has completed approximately 9 months of safety and effectiveness assessments post-surgery.

Refractive Error Stratified by Manifest Sphere and Cylinder						
			Cylii	nder (in minus n	otation)	
	0 Cylinder (Sphere Only)	-0.25 to - 0.5 D	-0.51 to -1 D	-1.01 to -2 D	-2.01 to -3 D	Total

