6.1.1 Fellow Eye Treatments

Because unilateral enrollment would result in subjects with a significant degree of anisometropia, and the safety and effectiveness of the TENEO 317 Model 2 excimer laser (ver. 1.28 US SW) specific to the treatment of myopia or myopic astigmatism are supported by retrospective data, bilateral LASIK treatments will be permitted in this study. Both eyes may be enrolled for effectiveness and safety assessments if the subject is fully informed that the surgical risks apply equally to each eye. If an intraoperative complication or adverse

event (AE) occurs in the first eye, treatment must be abandoned in the second eye. Each eye treated according to this protocol for an enrolled subject will be reported separately and included in the data analysis.

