The logMAR values will be converted to Snellen scores as follows:

Log MAR	Snellen Score
1.7	20 / 1000
1.6	20 / 800
1.5	20 / 630
1.4	20 / 500
1.3	20 / 400
1.2	20 / 320
1.1	20 / 250
1	20 / 200
0.9	20 / 160
0.8	20 / 125
0.7	20 / 100
0.6	20 / 80
0.5	20 / 63
0.4	20 / 50
0.3	20 / 40
0.2	20 / 32
0.1	20 / 25
0	20 / 20
-0.1	20 / 16
-0.2	20 / 12.5
-0.3	20 / 10

Once Δ MRSE and logMAR UCDVA are derived for all observations and the observations are categorized into response variables according to various MRSE and UCDVA thresholds

(e.g., MRSE within \pm 1.00 D), the imputed datasets are used to obtain the percentage of eyes that achieve MRSE predictability or UCDVA of 20/40 or better as follows:

PROC FREQ DATA=OUTDATA1; TABLES CRITERIA / BINOMIAL; BY IMPUTATION ; ODS OUTPUT BINOMIAL=PROP; RUN; DATA OUTDATA2; MERGE PROP (WHERE=(Label1="Proportion") RENAME=(nValue1=PROP)) PROP (WHERE=(Label1="ASE") RENAME=(nValue1=PROP SE)); BY IMPUTATION ; RUN; PROC MIANALYZE DATA=OUTDATA2; MODELEFFECTS PROP; STDERR PROP SE; BY VISIT; ODS OUTPUT PARAMETERESTIMATES=ESTIMATES; RUN;

where

- OUTDATA1 is the output dataset from PROC MI
- *CRITERIA* is a responder variable (either achieving MRSE predictability or UCDVA of 20/40 or better)
- OUTDATA2 is the output dataset containing the estimated proportion of responders and the standard error
- ESTIMATES is the results dataset

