6.5.6.2.1 Primary effectiveness endpoint hypothesis testing

All hypotheses will be tested at the one-sided 2.5% (α =0.025) level of statistical significance.

6.5.6.2.1.1 Percentage of eyes that achieve predictability of MRSE within ± 0.50 D at the time of refractive stability

The null hypothesis (H₀) is that the proportion of eyes that achieve predictability within \pm 0.50 D (π) is less than or equal to 0.80 (80%) at the time of refractive stability. The alternative hypothesis (H₁) is that the proportion is greater than 0.80 (80%).

$$H_0: \pi \le 0.80$$

 $H_1: \pi > 0.80$

The above hypothesis will be tested using CI calculated using normal approximation for binomial proportion. If the lower limit of the CI is above 0.8, then test is deemed significant.

6.5.6.2.1.2 Percentage of eyes that achieve predictability of MRSE within ± 1.00 D at the time of refractive stability

The null hypothesis (H₀) is that the proportion of eyes that achieve predictability within \pm 1.00 D (π) is less than or equal to 0.90 (90%) at the time of refractive stability. The alternative hypothesis (H₁) is that the proportion is greater than 0.90 (90%).

$$H_0: \pi \le 0.90$$

 $H_1: \pi > 0.90$

The above hypothesis will be tested using CI calculated using normal approximation for binomial proportion. If the lower limit of the CI is above 0.9, then test is deemed significant.

6.5.6.2.1.3 Percentage of eyes targeted for emmetropia that achieve UCDVA of 20/40 or better at the time of refractive stability

The null hypothesis (H₀) is that the proportion of eyes targeted for emmetropia and that achieve UCDVA of 20/40 or better at the time of refractive stability (π), is less than or equal to 0.88 (88%). The alternative hypothesis (H₁) is that the proportion is greater than 0.88 (88%).

$$H_0: \pi \le 0.88$$

 $H_1: \pi > 0.88$

The above hypothesis will be tested using CI calculated using normal approximation for binomial proportion. If the lower limit of the CI is above 0.88, then test is deemed significant.

6.5.6.2.1.4 Statistical Success Criteria for the Study

The study will be statistically successful if all primary effectiveness endpoints in this section are analyzed successfully (i.e., if the null hypotheses are rejected for all primary effectiveness endpoints) at the visit when cohort refractive stability is achieved.

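### The primary tests treat a subject's two eyes as independent, so the stated one-sided 2.5% error is not delivered if fellow-eye outcomes are positively correlated

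*SAP*

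**What the plan says.** SAP 6.1 states that "Both eyes of a subject may be enrolled", and SAP 6.1.1 that "bilateral LASIK treatments will be permitted in this study"; every treated eye enters the analysis. SAP 6.5.6.1 then sets the unit: "Eyes will be treated as independent sampling units ignoring any correlation between the two eyes of each subject". It calls this customary for LASIK trials and gives no other support.

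The primary code in SAP 6.5.6.2 takes the binomial proportion and its asymptotic standard error from each imputed dataset and pools them ("MODELEFFECTS PROP; STDERR PROP SE"). There is no subject term. For each endpoint SAP 6.5.6.2.1 says "The above hypothesis will be tested using CI calculated using normal approximation for binomial proportion", with success if the lower limit exceeds 0.80, 0.90 or 0.88, at one-sided 2.5%.

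The protocol synopsis says "each primary endpoint will be compared to a corresponding null proportion using a binomial test", but SAP section 4 says "The statistical analysis methods presented in this document will supersede the statistical analysis methods described in the clinical protocol", so the SAP rule governs. The sensitivity analyses (SAP 6.5.6.3 and 6.5.7.2) are observed or complete case, best case, worst case, site poolability, and complete case without the COVID-19 population.

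**The concern.** Fellow eyes share a patient, and the second eye may be treated straight after the first (Protocol Appendix C, 4.0). Positive correlation of outcomes is therefore plausible. Pairing is also likely to be common, because SAP 6.1.1 allows bilateral treatment in order to avoid leaving subjects anisometropic. With positive correlation the eye-level standard error is too small, the lower limit too high, and the true error of each test exceeds 2.5%. Nothing planned would show the reader by how much.

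The same applies to safety. The exact interval for serious device-related events (SAP 6.5.8.3) is computed on eyes, and SAP 6.5.8 names no method for its intervals. These are descriptive, but can look tighter than the number of subjects supports.

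**Working it through.** **Inputs from the documents.** One-sided alpha 0.025 (z = 1.960); nulls 0.80 (MRSE within 0.50 D), 0.88 (UCDVA 20/40 or better) and 0.90 (MRSE within 1.00 D); planned rates 0.945, 0.99 and 0.99; 300 evaluable of 334 treated eyes. Results are listed in that order of nulls.

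**Assumptions.** rho = 0.1 to 0.7 for the binary outcome in a pair; share of eyes in pairs f = 0.5 to 1. The base case is 300 complete eyes. Between-imputation variance is left out; it would widen the limits.

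**The plan's own figures.** Power = Φ[(p1 − p0 − 1.960·√(p0q0/n)) / √(p1q1/n)]. For 0.80 against 0.945, n = 300: (0.145 − 0.0453)/0.01316 = 7.58. The other two give 12.75 and 9.76. All exceed the stated 99.99%. The enrolment figure also reproduces: 300/0.90 = 333.3, so 334.

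**Step 1: clustering alone.** Design effect DE = 1 + f·rho; true level = 1 − Φ(1.960/√DE).

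| rho | half paired | all paired |
|---|---|---|
| 0.1 | 2.8% | 3.1% |
| 0.3 | 3.4% | 4.3% |
| 0.5 | 4.0% | 5.5% |
| 0.7 | 4.6% | 6.6% |

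For example, DE = 1.05 gives 1 − Φ(1.913) = 2.8%; DE = 1.70 gives 1 − Φ(1.503) = 6.6%.

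**Step 2: the governing SAP rule.** Exact enumeration with P(both succeed) = p² + rho·pq, P(one) = 2pq(1 − rho), P(neither) = q² + rho·pq, plus a binomial for single eyes. The rule passes at 253 / 274 / 279 of 300.

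| Setting (300 eyes) | 0.80 | 0.88 | 0.90 |
|---|---|---|---|
| independent eyes | 3.3% | 4.1% | 4.6% |
| rho 0.1, half paired | 3.6% | 4.5% | 5.0% |
| rho 0.5, half paired | 5.0% | 6.0% | 6.6% |
| rho 0.5, all paired | 6.7% | 7.9% | 8.6% |
| rho 0.7, all paired | 8.0% | 9.4% | 10.1% |

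The first row is the normal approximation on the proportion scale, not clustering. With all 334 treated eyes the figures are similar: 3.2 / 3.3 / 4.8% independent, and 6.6 / 6.8 / 8.8% at rho 0.5, all paired.

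**Step 3: the repaired rule.** A subject-clustered standard error on the logit scale gives 1.8% to 2.4% at the nulls over the pairing layouts examined (half to all eyes paired, rho 0 to 0.7). The same standard error left on the proportion scale gives 3.4% to 5.2%, so the scale must be named.

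**Step 4: effect on the verdict (150 pairs).** At the planned rates, the chance that the SAP rule passes and the repaired rule fails is at most 8 in a million at rho 0.5 and under 6 in 100,000 at rho 0.8. Power of the repaired rule at rho 0.8 is 99.996%, above 99.999% and 99.994%. At true rates of 85%, 91.5% and 93% with rho 0.5, power falls from about 64 / 58 / 55% to 42 / 31 / 27%.

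**Step 5: safety.** With no events, the exact 95% upper limit is 1 − 0.025^(1/300) = 1.2% on 300 eyes and 1 − 0.025^(1/150) = 2.4% on 150 subjects. The second is the bound under complete dependence.

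**The case against.** The choice is disclosed, and at the planned rates it would almost never change the result. Both are true. Disclosure does not make the stated 2.5% correct, however. The planned rates come from treatments "running PROSCAN ver. 1.27.2 SW for completing LASIK surgeries on myopic eyes with or without astigmatism through 1 month of follow-up"; Protocol 5.1 says the cylinder conversion factor was changed for version 1.28 US, and the test is at the stability visit. The margin is likely but not assured.

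The sizes rest on assumed rho and pairing. That stands: at rho 0.1 with half the eyes paired, clustering adds only 0.3 points in Step 1.

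The repair has a price. At the near-target rates in Step 4 the null is false, so each lost pass is lost power, not a false claim prevented. About 12 to 13 of the 22 to 28 points come from clustering and the rest from the change of scale. Part of this is the price of restoring 2.5%, since the planned rule's higher power there comes with 6.7 / 7.9 / 8.6% error.

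A single clustered sensitivity analysis would be cheaper and would show what the assumption costs, but it would leave the decision rule at an error rate it does not have.

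A reader might also infer that the protocol's binomial test protects the error. The documents do not support this. The synopsis does not call the test exact, Protocol 9.6.2 pools proportions and standard errors, and the SAP supersedes it. An exact binomial test, which no document names, could stay under 2.5% at small rho (1.9–2.6% at rho 0.1, half paired), but reaches 5.3–6.4% at rho 0.7, all paired.

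**Conclusion.** The point holds. The SAP ignores pairing, decides each primary test on an eye-level standard error and plans no check on it, so one-sided 2.5% is not delivered under positive inter-eye correlation. The presence of the problem is certain from the text; its size depends on rho and the paired share, which the documents do not give.

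Two stronger readings should be avoided. The 2.8–6.6% range is not the error of the planned rule: it isolates clustering in a test that is exact under independence. The planned rule has 3.6–5.0% error at the mild end of the assumptions and 8.0–10.1% at the severe end, partly from its separate scale defect. Nor do the documents suggest that the trial's conclusion is in doubt. All three endpoints must pass (SAP 6.5.7.5), so these rates are upper bounds on false overall success, and only results within a few eyes of a pass mark would change. It should be fixed because the correction is cheap, not because the result is likely to turn on it.

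**What to change.** Amend the SAP before database lock:

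- **6.5.6.1:** delete the independence sentence. State that the eye is the unit of summary and that standard errors, intervals and tests allow for eyes nested in subjects.
- **6.5.6.2:** in each imputed dataset estimate the eye-level proportion on the logit scale with a subject-clustered standard error (GEE with independence working correlation, or a survey procedure), and pool in PROC MIANALYZE.
- **6.5.6.2.1:** compare the back-transformed pooled lower 95% limit with 0.80, 0.90 and 0.88.
- **No failures:** the logit is then undefined. Pre-specify a conservative exact subject-level limit, and state that it stands in for the eye-level percentage. For 150 subjects with no failures it is 0.025^(1/150) = 97.6%.
- **Safety (6.5.8, 6.5.8.3):** put a subject-level exact or clustered interval, and the number of subjects, beside each eye-level interval.

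The cost is wording and a different SAS procedure; no extra eyes or visits. The primary estimate stays the eye-level percentage. Intervals widen, with the loss of power shown in Step 4 if true rates lie only just above target.
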